The PROMIS Assessment Center, the management tool within the larger PROMIS system, will be used to securely store de identified data, provide automated accrual reports and data export for this specific study. This study will have it's own study specific website.

Patients seen at the University of Virginia Cancer Center will be identified and invited to participate in an assessment of their reported outcomes over multiple domains available in PROMIS. Collecting this information on lung cancer survivors may provide a robust platform to design a patient-centered surveillance strategy following resection.

The study team hypothesizes that patient reported outcomes will vary according to the presence of recurrence or metastasis of lung or esophageal cancer. The study team also believes including patient reported outcomes into routine post-treatment surveillance will improve patient satisfaction and improve outcomes.

Background

1. Provide the scientific background, rationale and relevance of this project.

Lung cancer is the second most common cancer in both men and women in the United States. Of the estimated 182,550 patients newly diagnosed with non-small cell lung cancer (NSCLC) this year, approximately 35% will present with localized disease and be eligible for curative resection. For patients with limited NSCLC, surgical resection is the most effective method of controlling the primary tumor and provides the best opportunity for cure. The current standard of care is to perform a complete resection along with mediastinal lymph node sampling/dissection to accurately stage the patient, reduce local recurrence, and improve survival. A recent analysis by our group demonstrated that the number of lung cancer resections has increased over the past decade, with over 45,000 lung cancer resections performed annually in the United States.

Esophageal Cancer is one of the few cancers increasing in frequency in the US with 18,170 cases estimated for 2014. Unfortunately, the majority of these patients will ultimately die of their disease as the 5-year survival rate for all stages combined is 17%. The majority of these cancers are now adenocarcinomas of the distal esophagus and GE junction. Fortunately, more of these are being detected at an earlier stage when the chance of cure increases to over 50%. We perform over 50 esophagectomies each year at UVA and the majorities are now performed in a multidisciplinary fashion including treatment with chemotherapy and radiation.

The risk of lung and esophageal cancer recurrence varies widely from 30% to 75% and our group, along with others, has shown that recurrence depends upon a variety of tumor and patient related factors. For those patients whose recurrences are detected early, there is a possibility for long-term survival following redo surgical resection, radiation therapy or chemotherapy. However, the majority of patients with recurrence will not be candidates for curative treatment. Therefore, many patients undergo repeated surveillance testing to identify one patient whose survival can be meaningfully prolonged.

IRB-HSR# 17525 A Study of Patient-reported Outcomes in Patients with Lung or Esophageal Cancer

Therefore, the optimization of post treatment surveillance following lung or esophageal cancer resection is a national priority. The goal is to create a personalized decision support tool for lung and esophageal cancer surveillance that tailors follow-up to an individual patient. The decision tool incorporates risk-stratification for recurrence and survival, patient reported outcomes, and patient preferences to inform lung cancer survivors and their healthcare providers when selecting a surveillance strategy.

This observational study will look to see if the PROMIS score for each patient directly reflects the state of their disease by using these three disease states, no recurrence, asymptomatic with recurrence, symptomatic with recurrence.

Hypothesis to be Tested

Hypothesis: Patient reported outcomes will vary according to the presence of recurrence or metastasis in patients with lung or esophageal cancer.

Study Design: Biomedical

1. Will controls be used?

No

2. What is the study design?

Observational study

3. Does the study involve a placebo?

No

Human Participants

Ages: ≥18

Sex: Male or Female

Race: Any

Subjects- see below

1. Provide target # of subjects (at all sites) needed to complete protocol.

400

2. Describe expected rate of screen failure/ dropouts/withdrawals from all sites.

Expected rate of screen failures or dropouts is thought to be very low <%1

3. How many subjects will be enrolled at all sites?

400

4. How many subjects will sign a consent form under this UVa protocol?

400

5. Provide an estimated time line for the study.

IRB-HSR# 17525 A Study of Patient-reported Outcomes in Patients with Lung or Esophageal Cancer

50% enrollment in 6 months, 100% enrollment by end of year 1. There will be ongoing analysis of the data during the conduct of this trial.

Inclusion/Exclusion Criteria

1. List the criteria for inclusion

- ≥ 18 years of age
- Suspected or Known diagnosis of lung or esophageal cancer
- Willing and able to complete questionnaires
-

2. List the criteria for exclusion

- Subjects unwilling to provide informed consent
- Subjects unwilling or unable to answer the questionnaires

3. List any restrictions on use of other drugs or treatments.

None

Statistical Considerations

1. Is stratification/randomization involved?

NO

2. What are the statistical considerations for the protocol?

This is an observational pilot study to obtain patient reported outcomes for lung and esophageal cancer.

3. Provide a justification for the sample size used in this protocol.

The thoracic surgery and medical oncology clinics at UVa performed over 1,000 follow-up visits in 2012 for patients following lung and esophageal cancer resection. This pilot study will enroll 200 patients for integration of PCOR (Patient Centered Outcomes Research) score into their electronic medical record. A sample size of 150 patients is enough to detect a difference of 3.2 points on the PROMIS scale between each of the three groups (asymptomatic without recurrence, asymptomatic with recurrence, and symptomatic) with 80% power at the 5% significance level. (i.e.: if asymptomatic without recurrence averages 56.4, asymptomatic with recurrence averages 53.2 and, symptomatic with recurrence averages 50).

4. What is your plan for primary variable analysis?

This is an observational study to determine PROMIS scores at various time points. We will not be using repeated measures for this primary variable as each patient will only contribute one data point. We will calculate a mean and SD for each of the three disease states, no recurrence, asymptomatic with recurrence, symptomatic with recurrence.

5. What is your plan for secondary variable analysis?

We may do some longitudinal analysis of patient reported outcomes and will then account for repeated measures.

IRB-HSR# 17525 A Study of Patient-reported Outcomes in Patients with Lung or Esophageal Cancer

6. Have you been working with a statistician in designing this protocol?

Yes, [name]

Biomedical Research

1. What will be done in this protocol?

Enrolled subjects will be asked to complete an on-line (web-based) survey using an iPad or computer during a regularly scheduled clinic visit. This survey is estimated to take 10-15 min. Most patients will only be asked to complete this survey once, but some patients will be asked to answer the questions a second or third time during a regularly scheduled clinic visit for follow up of their esophageal or lung cancer.

Patients will provide their age, race, ethnicity and sex at the beginning of the survey. They will be provided a unique study identifier (i.e., 001, 002 etc.) and a password that they can use to complete the survey. Only the patient will have access to the password and no HIPPA identifiers are collected in the PROMIS on-line system. A Private web browser will be used to access the PROMIS website for each patient, so that all web browsing activity is removed after each patient completes the survey. A member of the research team will be responsible for closing the web based session in order to make sure all browsing history is erased properly."

Data will then be collected from the STS Society of Thoracic Surgeons database for subjects who complete the on-line survey. The STS database is a national quality improvement database which the University of Virginia participates in for clinical purposes. Local data from the STS database will be queried for subjects who are enrolled in this study to provide clinical information about the patients clinical condition. The PROMIS reports and the STS data that links clinical information with the PROMIS data will be stored on a HIPPA compliant UVA server (surgery O: drive). This data will be accessible only to members of this research team.

Paper Case report forms for eligibility verification, consent process documentation and enrollment verification may be maintained in paper format. Paper case reports forms will be stored in a limited access office and in a locked file cabinet.

2. List the procedures, in bullet form, that will be done for research as stipulated in this protocol.

- Enrolled subjects will be asked to complete an on-line (web-based) survey using an iPad or computer. This survey is estimated to take 10-15 min. Most patients will only be asked to complete this survey once, but some patients will be asked to answer the questions a second or third time over a maximum five year period.
- Information to be collected from the STS Database will include:
 - Subject Name

IRB-HSR# 17525 A Study of Patient-reported Outcomes in Patients with Lung or Esophageal Cancer

- Subject medical record number
- Age
- Gender
- Race
- Pathology, laboratory/microbiology results
- Medications
- Vital signs, Height, weight, other clinical parameters.
- Perioperative Data
- Diagnosis
- Comorbidities
- Surgical procedure performed
- Date of surgery
- Surgical approach
- Date of Discharge
- Cancer stage, recurrence or metastasis sites

3. Will you be using data/specimens in this study that were collected previously, with the use of a research consent form, from another research study?

No

4. Will any of the procedures listed in item # 2 have the potential to identify an incidental finding?

Yes

X This examination(s) utilizes non-standard/investigational, technique, equipment, etc. It is impossible to determine the significance of such results, therefore abnormalities will not be shared with the subject because the meaning of the exam is not yet proven and is of unknown clinical benefit.

5. Do any of the procedures listed above, under question # 2, utilize any imaging procedures?

NO

6. Will you be using viable embryos?

NO

7. Will you be using embryonic stem cells?

NO

8. Are any aspects of the study kept secret from the participants?

NO

9. Is any deception used in the study?

NO

IRB-HSR# 17525 A Study of Patient-reported Outcomes in Patients with Lung or Esophageal Cancer

Cancer Center Protocol Review Committee (PRC) Requirements

1. Designate type of study

CHECK ONE	TYPE of SPONSOR	Oversight by CC DSMC?	External DSMB Required?	Additional Requirements
X	UVa Investigator Initiated- Single site at UVa	No	Not required by PRC.	
• Enrollment/ accrual information must be submitted to OnCore. **

1. What is the risk level of this study?

Check One	Risk Level	Examples	Monitoring Frequency by CC DSMC, VPR Post Approval Compliance Monitors	Additional Requirements
X	PRC review not required	
• Epidemiology research,• Surveys,• Database protocols• Protocols using discarded tissue• Any other protocols involving cancer patients that do not have cancer focus.	N/A – studies not monitored by the CC DSMC	

Data and Safety Monitoring Plan

This study has been deemed minimal risk. Because this study poses minimal risk to the subject, **adverse events will only be collected or recorded if a causal relationship to the study intervention is suspected**. If any adverse event is considered serious and unexpected, the event must be reported to the IRB-HSR within 7 days from the time the study team receives knowledge of the event.

1. Definitions

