DHHS: Study team requests a Waiver of Consent to contact potential subjects.

HIPPA: NA

3. **Will any additional information be obtained from a potential subject during "prescreening"?**

NO

4. **Do you plan to ask the subjects to do anything, other than answering questions, for the study prior to signing a consent?**

NO

5. **How will the consenting process take place with either the prospective subject, the subject's legally authorized representative or parent/legal guardian of a minor (if applicable)?**

Subjects will be approached at UVA about participation in this study. A member of the study team will review the informed consent with the subject, and facilitate a discussion of the study procedures, risks/benefits, and alternatives. Subjects will be told that their participation is voluntary – and they do not have to participate in this study. Subjects will also be informed that their decision to participate or not participate will not influence the medical care they receive at UVA.

Subjects will be given the opportunity to take the consent home for consideration if they desire, and questions will be answered. The physician investigator will be available to address questions; however consent will be primarily obtained by the study coordinators. Subjects who wish to participate will be asked to sign the consent form prior to any data being collected. A copy of the signed consent form will be given to the subject.

IRB-HSR# 17525 A Study of Patient-reported Outcomes in Patients with Lung or Esophageal Cancer

6. Will subjects sign a consent form for any part of the study?

yes

7. Will the study procedures be started the same day the subject is recruited for the study?

Subjects will be recruited in the thoracic surgery clinic during routine visits.

Subjects may be asked to complete the questionnaires/survey on the same day as they are signing informed consent, however, will be given the option of completing the baseline questionnaires at a later date as time permits.

► IF YES, explain in detail why the subject cannot be given more time to make a decision to consent.

Subjects will be given adequate time to consider participation in this observational study. Subjects will be given the opportunity to take the consent home and consider participation at a later date.

► IF YES, explain in detail what will be done to assure the potential subject has enough time to make an informed decision.

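### The 80% power claim at 150 patients gives no SD, test or group sizes; with an assumed SD of 10 it fits an overall three-group test with fairly balanced groups, not the pairwise differences it describes

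*Combined protocol and SAP*

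**What the plan says.** Statistical Considerations, item 3, claims that "A sample size of 150 patients is enough to detect a difference of 3.2 points on the PROMIS scale", and applies this "between each of the three groups (asymptomatic without recurrence, asymptomatic with recurrence, and symptomatic"), "with 80% power at the 5% significance level". The illustration is "if asymptomatic without recurrence averages 56.4, asymptomatic with recurrence averages 53.2 and, symptomatic with recurrence averages 50". Adjacent states therefore differ by 3.2 points and the extremes by 6.4. No SD, test, multiplicity rule or group size is given.

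Item 4 of the same section is descriptive: "We will calculate a mean and SD for each of the three disease states". It names no test either.

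On the mix of states, the question "Is stratification/randomization involved" is answered no. Entry requires only a suspected or known diagnosis of lung or esophageal cancer, and the Recruitment appendix, item 7, says "Subjects will be recruited in the thoracic surgery clinic during routine visits". No section sets a target, cap or minimum by disease state. The only recurrence figure is in the Background: "The risk of lung and esophageal cancer recurrence varies widely from 30% to 75" per cent. It is a risk, not the share of clinic attendees who have recurrence, and no asymptomatic/symptomatic split is given.

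Three sample sizes appear. The Human Participants answers on target, enrolment and consent all say 400. Item 3 says 200 will be enrolled, and calls 150 enough.

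**The concern.** The wording promises power for each difference between states. The natural way to arrive at 150 is three groups of 50 and one overall test, which is a different promise. The mix is also left to whoever attends clinic, so the two recurrence groups may be much smaller than 50.

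The study asks whether the score reflects three disease states, with surveillance as the intended use. Patients with recurrence but no symptoms matter most to that use, and they could form one of the smallest groups. A reader who takes item 3 at face value would treat a null result for an adjacent pair as informative when it may have had little chance of being positive.

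**Working it through.** **Inputs.** From item 3: means 56.4, 53.2 and 50; alpha 5%; power 80%; N = 150. From the Background: recurrence risk 30% to 75%. Assumed, because the documents are silent: SD 10 (8 to 12 also examined), two-sided tests, no multiplicity adjustment, and an even split of recurrences unless stated. Fractional group sizes are kept as they fall.

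**Overall test.** λ = Σ nᵢ(μᵢ − μ̄)² / SD², with μ̄ the weighted mean. Power is the chance that a noncentral F with 2 and N − 3 degrees of freedom exceeds its 5% critical value.

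*The plan's figure.* At 50/50/50, μ̄ = 53.2 and λ = (50 × 3.2² + 0 + 50 × 3.2²)/100 = 10.24. The critical value is 3.058 and power is 81.7%. The smallest equal-group total reaching 80% is 147 (49 each). So 150 and 80% fit this reading. With SD 8, 9, 10, 11 and 12, power is 95%, 89%, 82%, 73% and 65%.

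*30% recurrence at 150.* At 105/22.5/22.5, μ̄ = 54.96 and λ = (105 × 1.44² + 22.5 × 1.76² + 22.5 × 4.96²)/100 = 8.41. Power is 73%.

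*Other mixes (no recurrence / asymptomatic / symptomatic), SD 10:*

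| N | Mix | Overall power |
|---|---|---|
| 150 | 75/37.5/37.5 (50% recurrence) | 83% |
| 150 | 37.5/56.25/56.25 (75%) | 78% |
| 150 | 105/13.5/31.5 | 82% |
| 150 | 105/15/30 | 81% |
| 150 | 105/30/15 | 63% |
| 200 | 140/30/30 (30%) | 85% |
| 400 | 280/60/60 (30%) | 99% |
| 400 | 360/20/20 (10%) | 78% |

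More lopsided splits of the 45 recurrences widen the range: 44% if nine in ten are asymptomatic, 88% if one in ten is.

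**Pairwise test of 3.2 points.** The noncentrality is 3.2 / (SD × √(1/a + 1/b)) for group sizes a and b, in a two-sample t test.

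- SD 10, 50 v 50: 3.2/(10 × 0.2) = 1.60, power 35%.
- SD 10, N = 400 at 280/60/60: no recurrence v asymptomatic has noncentrality 2.25, power 61%. Asymptomatic v symptomatic has 1.75, power 41%.
- SD 10, 80% power: about 154 per group by the normal approximation, so 3 × 154 = 462 in all, more than the planned 400.

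*What SD would make the claim true pairwise?* With 50 per group, SD = 3.2 / ((1.960 + 0.842) × √(2/50)) = 5.71 by the normal approximation (the t test gives 79% there). Holding SD at 5.71 with 30% recurrence and an even split, asymptomatic v symptomatic has:

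- N = 150 (22.5 v 22.5): noncentrality 1.88, power 45%
- N = 200 (30 v 30): 2.17, power 57%
- N = 400 (60 v 60): 3.07, power 86%

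**The case against.** The strongest reply is that 150 is not the planned size. Enrolment is 400 in three answers and 200 in item 3, and at 30% recurrence with an even split the overall test has 85% and 99% power there. A reader might infer that the study as planned misses its stated 80%. On the overall test the documents do not support that: at 400 it drops below 80% only when about 10% of patients have recurrence.

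A reader might also infer that 50 in each state is required. For the overall test it is not, since 75/37.5/37.5 does slightly better than 50/50/50. Nor does the plan's own risk figure imply 105/22/22. Thirty per cent is the bottom of a wide range, it is a risk rather than a share at visits, and the even split is an assumption. With fewer asymptomatic recurrences (105/15/30) the overall test still reaches 81%.

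Finally, if the claim is pairwise and SD is 10, balance alone does not rescue it: power is 35% at 50 per group. The main gap is then the missing SD and test, with the mix second. The study is also a pilot with a descriptive primary analysis.

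All of this stands. It does not answer the point that an explicit power statement, worded as applying to each difference, cannot be checked from its stated inputs, and that no group size behind it is secured.

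**Conclusion.** The claim as worded is not supported. With an SD near 10 it describes one overall test with fairly balanced groups: at 150 patients, roughly 40% to 70% recurrence, evenly split, keeps power at 80% or above. At 30% recurrence it is about 73% with an even split, and 63% to 82% for the splits between 105/30/15 and 105/13.5/31.5. The adjacent pairs fall well short, at about 35% with 50 per group and 61% and 41% at 400 with 30% recurrence. If the claim is meant pairwise, it needs an SD near 5.7 and about 50 in every state. On that reading, at 30% recurrence and an even split, 200 patients fall short for asymptomatic v symptomatic recurrence (57%), while 400 suffice (86%).

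This does not show that the study is too small for an overall comparison. The figures rest on an assumed SD, an assumed split of recurrences and a recurrence share at visits that the documents do not give.

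**What to change.** In item 3:

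- Reconcile 150, 200 and 400, and base the justification on the number actually planned.
- Say that the 80% refers to the overall three-group test, and state the SD and group sizes assumed.
- Replace the wording "between each of the three groups (asymptomatic without recurrence, asymptomatic with recurrence, and symptomatic") with the pairwise power at the planned N, tabulated over a range of recurrence shares and SDs.

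In enrolment, keep a running count by disease state. Within the planned 400, hold places so that each recurrence state reaches at least 50 where feasible, the number the calculation implies. That is 100 of 400, or 25%. At 300/50/50 the overall test has λ = 19.84 and 98% power. Asymptomatic v symptomatic would still have only about 35% if SD is 10, so the minimum guards against very small groups and does not replace the pairwise table.

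Cost: protocol wording and a simple tally, with no more patients than the 400 already planned. The stated power becomes less favourable. Accrual may run beyond the one-year timeline, especially if symptom status is hard to establish before approach. Whole-clinic summaries would then need weighting by state. A stricter cap on patients without recurrence is harder to justify: 160/120/120 would need 240 patients with recurrence from clinics reporting just over 1,000 follow-up visits (not patients) in a year.

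### Disease-state means are compared without regard to time since surgery, so post-operative recovery could narrow the gap between no recurrence and recurrence by an amount the documents do not allow one to fix

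*Combined protocol and SAP*

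**What the plan says.** Item 4 of Statistical Considerations describes the primary variable in these terms: "This is an observational study to determine PROMIS scores at various time points". It adds that "each patient will only contribute one data point", and the whole analysis is: "We will calculate a mean and SD for each of the three disease states, no recurrence, asymptomatic with recurrence, symptomatic with recurrence". No covariate, stratum or survey window is given. Item 5 allows an optional longitudinal analysis that would handle repeated measures; it does not bring time since surgery into the primary comparison.

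On timing, the Recruitment appendix (item 7) says "Subjects will be recruited in the thoracic surgery clinic during routine visits", and the inclusion criteria set no minimum time after resection. Among the STS fields listed under Biomedical Research, item 2, is "Date of surgery"; no analysis is said to use it.

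The sample size paragraph (item 3) states: "A sample size of 150 patients is enough to detect a difference of 3.2 points on the PROMIS scale between each of the three groups", "with 80% power at the 5% significance level", with the example "if asymptomatic without recurrence averages 56.4, asymptomatic with recurrence averages 53.2 and, symptomatic with recurrence averages 50". Its first group is therefore patients who are both free of symptoms and free of recurrence, whereas item 4 speaks only of no recurrence.

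**The concern.** The stated hypothesis is that reported outcomes vary with recurrence or metastasis, so anything linked to both disease state and score bears on the answer. Time since surgery is a candidate for both. Recurrence is found some time after resection, so patients surveyed shortly after the operation will mostly be classed as recurrence-free. Those same patients may report worse function because they are still recovering from lung resection or esophagectomy. With one score per patient, nobody serves as their own control.

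If this happens, the no-recurrence mean shifts towards the recurrence means for reasons unrelated to disease state. The step most exposed is no recurrence against asymptomatic recurrence, which is also the step that matters most for a surveillance tool meant to add something before symptoms appear. Enrolling more patients would not remove the bias.

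**Working it through.** **1. The plan's own figure.** Inputs from item 3: means 56.4, 53.2 and 50; 150 patients; 5% level; 80% power. Two inputs are not in the document and are assumed: 50 patients per state and an SD of 10. For a one-way ANOVA F test with 2 and 147 degrees of freedom, the noncentrality is

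λ = n × Σ(mean − grand mean)² / SD² = 50 × (3.2² + 0² + 3.2²) / 10² = 10.24,

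which gives 81.7% power. On these assumptions the stated 80% is reproduced for the overall test. The result depends on the SD: power is 95% at SD 8 and 65% at SD 12.

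**2. Bias formula.** Let p₁ be the share of early surveys in the no-recurrence group, p₂ the share in each recurrence group, and d the number of points by which recovery lowers an early score. Then

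bias in the no-recurrence contrasts = (p₁ − p₂) × d, and the first step becomes 3.2 − bias.

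The documents give none of p₁, p₂ or d. The values below are assumptions chosen to show a range. Power is for the overall test with the no-recurrence mean lowered by the bias, SD kept at 10, and the extra spread from mixing early and late patients ignored.

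| p₁ v p₂ | d | Bias | Bias / 3.2 | First step left | Overall power |
|---|---|---|---|---|---|
| 10% v 5% | 3 | 0.05 × 3 = 0.15 | 5% | 3.05 | 80% |
| 10% v 5% | 10 | 0.05 × 10 = 0.50 | 16% | 2.70 | 75% |
| 20% v 5% | 5 | 0.15 × 5 = 0.75 | 23% | 2.45 | 71% |
| 20% v 5% | 10 | 0.15 × 10 = 1.50 | 47% | 1.70 | 59% |
| 40% v 5% | 5 | 0.35 × 5 = 1.75 | 55% | 1.45 | 55% |
| 40% v 5% | 10 | 0.35 × 10 = 3.50 | 109% | −0.30 | 33% |

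Example for the top row: the means become 56.25, 53.2 and 50, the grand mean is 53.15, and λ = 0.5 × (3.10² + 0.05² + 3.15²) = 9.77. For the bottom row: 52.9, 53.2 and 50, and λ = 3.12.

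The first step disappears when (p₁ − p₂) × d = 3.2. With equal p₂ in both recurrence groups, the step from 53.2 to 50 does not change in any row.

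**3. Precision cost of adjusting.** Take the heaviest shares: 20 of 50 early without recurrence, 5 of 100 early with recurrence. The correlation between the early indicator and the no-recurrence indicator is

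φ = (20 × 95 − 30 × 5) / √(50 × 100 × 25 × 125) = 1750 / 3953 = 0.44,

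so the variance inflation is 1 / (1 − 0.196) = 1.24, about 20% of the information on that contrast, before any gain from lower residual variance.

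**The case against.** The strongest reply is that the concentration of early surveys in the no-recurrence group is inferred. The clinics performed over 1,000 follow-up visits in a year, and repeat surveys may extend to five years, so early visits could be a small share. At 10% against 5% with a 3-point effect, the bias is 0.15 points, which is negligible. This stands: the size cannot be settled from the documents.

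Second, the 3.2 points are planned against patients without symptoms or recurrence. If that definition governs, recently operated patients who still have symptoms would not clearly belong in the top group, and some of the contamination falls away. This also stands, but it exposes a mismatch between items 3 and 4 that needs settling in any case.

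Third, no PROMIS domain is named as primary. The downward pull follows the example in item 3, where higher is better. On a scale where higher is worse, recovery would push the no-recurrence mean up, still towards the recurrence groups. A domain that surgery does not worsen would show no such narrowing. One effect size cannot be carried across domains.

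Fourth, the raw association at routine visits is itself a defensible target for a surveillance tool, and the study is a pilot whose item 4 is descriptive. That is a reason to keep the raw means. It does not make them sufficient, because the protocol also states a hypothesis about recurrence and powers a difference between states.

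A reader might go further and infer that the study would find no relation between PROMIS and recurrence because of post-operative recovery alone. The documents do not support that. They give no early shares and no recovery effect, only the most extreme assumptions above remove the first step, and the step between asymptomatic and symptomatic recurrence is left intact when early shares are equal in those groups.

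**Conclusion.** The point holds as a possible confounder of unknown size. The facts are plain from the text: unadjusted means, unrestricted survey timing, and a surgery date that is collected but not used. That early surveys fall mostly in the no-recurrence group is a reasonable inference from how recurrence arises, not something the protocol states. Under the assumed ranges the bias is 0.15 to 3.5 points against a planned 3.2, so it could be trivial or could remove the first step. The direction assumes a domain that recovery worsens, and the power figures assume SD 10 and 50 patients per state. This is a worthwhile, inexpensive improvement to the analysis; it does not show that the planned comparison will fail.

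**What to change.** In item 4:

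- Keep the raw mean and SD per disease state. Beside them, for patients whose resection preceded the survey, give disease-state means from a linear model with time from surgery to survey (early/late bands or a spline), age and sex. Fix the bands before results are examined, since the protocol foresees ongoing analysis during the study.
- Record the survey date. It is not among the listed data items, although the web system may hold it.
- Report the distribution of time since surgery by disease state, and add a sensitivity analysis that drops the early surveys.
- Report patients with no operation, or surveyed before it, as a separate category. Suspected cancer is eligible and the Recruitment appendix mentions baseline questionnaires, so a time-since-surgery model would otherwise drop them without notice.
- Use one definition of the no-recurrence group in items 3 and 4, and name the PROMIS domain to which the comparison applies.

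Other extracted variables, such as stage and comorbidities, could be argued for as covariates; the set above is a minimum.

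The cost is analysis wording and one date field. There is some loss of precision on the no-recurrence contrast: variance inflation of about 1.24 if 40% against 5% are early, and less if the shares are closer. Early recurrences will be few, so the adjusted contrast in the early band will lean on the model; this is a further reason to show both sets of means.
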